## **Table 29 Template for Describing DLT Rates**

DL Cohort (Dosing Sequences)	Number FAS	Number DLT Evaluable	Number DLTs	DLT Rate
$a/b/c^*$ mg				
a/b/c/d* mg				
$b/c/d^*$ mg				
Supplementary DLT Rates for Period-Specific Dose Levels		I		
1st dose: a mg				
1st dose: b mg				
2 nd dose: b mg				
2 nd dose: c mg				
3 rd dose: c mg				
3 rd dose: d mg				
4 th dose: d mg				

\* prime/lower intermediate (/higher intermediate)/full dose numbered as: 1 st dose/2nd dose/3rd dose/3rd dose/3rd dose/3rd dose/4th dose.

1.1 Preface

The objective of this document is to detail the statistical methodology to be used for the planned analyses of the Escalation Part GCT1044-01, for the development of GEN1044 for the treatment of solid tumors (which induces T-cell mediated cytotoxicity of 5T4-expressing tumor cells by crosslinking CD3 on T cells with the tumor-associated antigen 5T4 on tumor cells).

This statistical analysis plan (SAP) is based on the following information and documents:

Trial Protocol	03 Apr 2020 – version 3.0 (Amendment 2)	
Trial Protocol	30 Mar 2021; v4.0 (Amendment 3)	
Unique Case Report Forms (CRFs)	07 Jul 2021 eCRF_Final_5.0	

Layouts, programming notes and titles for the tables, listings and figures are further specified in the DPS.

1.2 Timing of statistical analyses

Upon review and evaluation of the overall safety profile and safety signals of GEN1044 on 29 September 2021, Genmab Safety Committee classified pneumonitis as an important identified risk for GEN1044. Given this, further enrollment was stopped into GCT1044-01.

GEN1044 was tested in with a prime dose, followed by up to one intermediate dose, and then full doses until treatment discontinuation. The data will be summarized by the cohorts presented in Table 1.

		1 st Intermediate	2 nd Intermediate	
	Priming Dose	Dose	Dose / Full Dose	Full dose
Cohort	(C1D1)	(C1D8)	(C1D15)	(C2D1)
0.3/3/3 mg	0.3	3	3	3
1/5/5 mg	1	5	5	5
1/3/10 mg	1	3	10	10
1/3/30 mg	1	3	30	30
1/5/30 mg	1	5	30	30
1/10/30 mg	1	10	30	30
1/5/30/37.5 mg*	1	5	(30)	(37.5)
1/5/45 mg**	1	5	45	45
1/3/60 mg	1	3	60	60

Table 1: Dose Escalation Cohorts

2 Modification History

2.1 Changes to the trial protocol

Efficacy endpoints will only be listed by subject and timepoint, they will not be summarized in the CSR.

2.2 Changes to previous SAP versions

Due to the early termination of GCT1044-01 it was also decided to write an abbreviated CSR including key safety information (as would be included in a full CSR), whereas efficacy information and information in other sections should be concise and not as comprehensive as in a full CSR. Furthermore, all analyses for the expansion part were deleted as no expansion data was collected.

This SAP version describes the analysis required for the abbreviated CSR.

3 Trial Design

The conceptual trial design is visualized in Figure 1. The trial was planned as a two-part trial, with an escalation part followed by an expansion part. This analysis plan incorporates the planned analyses Escalation Part only, as required for the abbreviated CSR.

DL = dose level, DLT = dose-limiting toxicity, RP2D = recommended phase 2 dose.

In the Escalation Part, GEN1044 was administered by intravenous (IV) infusions at increasing dose levels, see Table 1.

3.1 Primary objectives and endpoints

Table 2: Objectives and Endpoints

Objectives			Endpoints
Primary			
•	Determine recommended phase 2 dose (RP2D)	•	Dose-limiting Toxicities (DLTs)
•	Establish safety profile of GEN1044	•	Adverse events (AEs) and safety laboratory parameters
Se	condary		
•	Establish PK profile	•	PK parameters (clearance; volume of distribution; area under the concentration-time curve (AUC) from time zero to last quantifiable sample (AUC _{last}) and from time zero to infinity (AUC _{inf}); maximum (peak) observed serum drug concentration (C _{max}); time to reach maximum (peak) serum drug concentration (T _{max}); predose trough concentrations (C _{Trough}); and elimination half-life (T _{1/2}).
•	Evaluate immunogenicity of GEN1044	•	Anti-drug antibody (ADA) response
•	Evaluate anti-tumor activity based on response assessment criteria (RECIST v1.1)	•	 Anti-tumor activity, ie, reduction in tumor size according to response assessment (RECIST v1.1): Objective response rate (ORR) Disease control rate (DCR) Duration of response (DOR) Time to response (TTR)
Exploratory			
•	Assess pharmacodynamics and potential biomarkers of GEN1044	•	Immune system activation (eg, T-cell activation, cytokine production,), expression of tumor targets (eg, 5T4and potential biomarkers)
•	Assess anti-tumor activity based on iRECIST	•	Anti-tumor activity, ie, reduction in tumor size according to iRECIST o Immune ORR (iORR) o Immune DCR (iDCR) o Immune DOR (iDOR)
•	For prostate cancer subjects only: Assess anti- tumor activity based on Prostate Cancer Working Group 3 (PCWG3)-Modified Response Evaluation Criteria in Solid Tumors (mRECIST) 1.1	•	 Anti-tumor activity, ie, reduction in tumor size according to RECIST v1.1 modified by PCWG3 for bone lesions Modified ORR (mORR) Modified DCR (mDCR) Modified DOR (mDOR) Composite response rate (CRR)
•	For prostate cancer subjects only: Assess changes in prostate-specific antigen (PSA) from baseline	•	PSA response PSA progression

3.2 Sample size

Escalation Part

The mBOIN design, as described in Section 4.2.1.1 of the protocol, will enrol up to 58 subjects. Enrolment may be halted based on the pre-specified stopping rules as described in Section 4.2.1 of the protocol.

The initial cohort size is single subject. The cohort size will be expanded to 3 subject cohorts if a DLT or Grade \geq 2 AE within the first 21 days of Cycle 1 is observed in a single subject cohort. (After this, all subsequent cohorts are planned as 3 subject cohorts.) Further details are provided in Section 4.2 of the protocol.

3.3 Treatment administration schedule

GEN1044 will be infused intravenously in 21-day cycles, as per Section 4.1 of the protocol:

- Cycle 1-4: Day 1, 8, and 15
- Cycles 5 and later: Day 1 only

3.4 Treatment assignment

Subjects will be enrolled into pre-defined dose cohort during the Escalation Part.

4 Analysis Sets

Enrolled Subjects

Enrolled Subjects include all subjects whose treatment were assigned.

Full Analysis Set (FAS)

The full analysis set (FAS) and safety set are defined in the same way and will comprise all subjects who receive at least 1 dose of trial drug. All subjects will be classified according to the dose level and treatment schedule (if applicable) which they were assigned.

Safety Set (SAF) / Treated Set

The Safety set is the same as the FAS.

Dose-Determining Analysis Set (DDS)

The Dose-Determining Set (DDS) includes all FAS subjects in the Escalation Part who meet the minimum exposure criterion and have sufficient safety evaluations or experience a DLT during the first 21 days of dosing (i.e., in Cycle 1).

A subject will meet the minimum exposure criterion if the subject takes at least 2 out of 3 pre-planned doses during the DLT period (such as 1 priming dose and 1 full dose).

A subject will have sufficient safety evaluations if the subject has been observed for \geq 21 days following the first dose and are considered by both the sponsor and investigators to have enough safety data to conclude that a DLT did not occur.

Subjects will be analyzed according to the trial treatment received, as defined for the FAS.

5 General Statistical Methods and Definitions

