#### 11.1.7 Dose-Determining Analysis Set – Dose Escalation Part

The dose-determining set (DDS), which is used to define the number of DLT evaluable subjects on a DL cohort, will include all FAS subjects in the escalation part who meet the exposure criterion (defined below) and have sufficient safety evaluations, or experience a DLT prior to the 2nd full dose administration. The DLT period will extend until 7 days after the first full dose (see Section 4.2).

A subject meets the exposure criterion if all doses, up to and including the 1st full dose, are administered in a timely fashion: In general, the individual doses should not be delayed more than 7 days. However, longer dose delays might be acceptable if the DEC considers the assessments still to be appropriate. The first full dose should be administered at latest by 30 calendar days after C1D1 (if one intermediate dose is administered), or by 38 calendar days after C1D1 (if two intermediate doses are administered), counting the day of first exposure as C1D1.

If there is a longer dose delay the subject is considered as non-DLT evaluable (as long as the reason for the dose delay, or the dose delay itself, is not classified as a DLT). DLTs occurring beyond the DLT period will be presented, but not contribute to the DLT rates for the DL cohort per mBOIN.

Subjects who do not experience a DLT will be considered to have sufficient safety evaluations if they have been observed for  $\ge 21$  days (or  $\ge 28$  days if 2 intermediate doses are applied) following the priming dose, and are considered by both the sponsor and investigators to have enough safety data to conclude that a DLT did not occur.

For a period-specific dose level (doses up to and including 1st full dose), a subject is considered as DLT evaluable if the dose was timely administered (ie, not delayed for more than 7 days) and had sufficient safety evaluations up to the subsequent dose administration to conclude if a DLT did occur or not. The relative DLT periods for priming and intermediate doses extend the planned timing of the subsequent dosing (ie, extends until 7 days after the dose administration). For the 1st full dose, it extends up to 7 days past drug administration. Appendix 9 provides a comparison of the DDS considerations and a template for the reporting of DLT rates.

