# 11.5.2 Primary Endpoint – Dose Limiting Toxicities

The number of DLTs during the DLT period will be observed, as part of determining the RP2D.

The number treated per FAS, number of DLT evaluable subjects, number of DLTs, and DLT rate on each DL cohort will be tabulated.

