## **Appendix 8 Recommended ICANS Management**

Source: (Garcia Borrega et al., 2019; Lee et al., 2019)

<sup>2 Borrega Garcia et al., 2019.

Version: 4.0

## Appendix 9 Description of DLT Rates After Protocol Amendment 3

Table 28 Dose-Determining Analysis Sets Comparison

DLT Consideration	Number FAS	Number DLT Evaluable	DLT Period	Comment
DL cohort	All those with at least 1 dose (ie, prime dose) administered	All those who meet the exposure criteria for the DL cohort, or experience a DLT during the DLT period	Up to 7 days past 1 st full dose administration	Regardless of what individual dose that the DLT could be associated with, the DLT is attributed to DL cohort as such
Period-specific DLT rates	All those administered the period-specific dose	All those administered the period-specific dose in a timely fashion	Up to 7 days past dose administration	

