5.1 General statistical methods

The statistical analyses will be presented by dose level cohort, for the different analysis sets as defined in Section 4.

In general, continuous variables will be summarised using descriptive statistics, i.e. displaying number of subjects in the respective analysis population, number of subjects with data, number of subjects with missing values, mean, standard deviation, minimum, median, and maximum.

Categorical variables will be summarised by using frequency counts and percentages. In addition, the number of subjects with missing values will be displayed where appropriate. When the number of subjects with non-missing values is displayed by visit (i.e., the number of subjects with a certain assessment completed at a given visit), that number will be used to calculate the percentages for that visit. Otherwise, the number in the column header (e.g., the number in that cohort, etc.) will be used as the denominator unless otherwise specified.

Means, medians, and standard deviations will be presented by 1 additional decimal place more than the standard presentation level of the respective subject data. Minimum and maximum values will be presented using the same number of decimal places as the subject data. Percentages will be presented to 1 decimal place if not otherwise stated.

If the number of subjects in a category is 0, then the percentage will not be displayed, and only a count of 0 will be shown.

Figures will be presented as necessary. Unless otherwise specified, by-visit figures will display information as presented in tables (e.g., based on analysis visit). Time-to-event figures, profile plots, and other figures not based on specific visits will include unscheduled visits.

Unless otherwise specified, all subject data collected as part of this trial (CRF data, laboratory results, etc.) will be presented in data listings. In general, data will be sorted by dose level cohort or tumor type cohort (as appropriate), site, and subject, and when appropriate by visit or other identifiers for sequence or type of observation.

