6.1 Subject accounting

The number and percentages of subjects in each analysis set as defined in Section 4 will be presented by dose level cohort.

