9.1 Primary safety analysis

Dose-Limiting Toxicities (DLTs)

The primary endpoint for the Escalation Part of this trial is the DLTs. Adverse events (AEs) that are assessed by the investigator to be at least possibly related to GEN1044, which occur during the DLT period of the Escalation Part. DLT will be summarized by PT in order of descending frequency using Dose-Determining Analysis Set.

The distribution of DLT occurring at the dose level will be plotted by subjects.

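### The SAP's dose-determining set accepts any 2 of 3 planned doses, while protocol v4.0 asks for every dose through the first full dose, given on time; the difference is undeclared and can inflate the DLT-evaluable number

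*SAP*

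**What the plan says.** **SAP, section 4 (Dose-Determining Analysis Set).** "A subject will meet the minimum exposure criterion if the subject takes at least 2 out of 3 pre-planned doses during the DLT period". One priming plus one full dose is given as an example only. A DLT-free subject also needs at least 21 days of observation and agreement between sponsor and investigators that the data suffice. A DLT in the first 21 days is the other way in.

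**Protocol v4.0, section 11.1.7.** "A subject meets the exposure criterion if all doses, up to and including the" first full dose, are given on time. In general no dose may be more than 7 days late, but the DEC may accept longer delays. Appendix 9, Table 28 defines the evaluable subjects of a DL cohort the same way: "All those who meet the exposure criteria for the DL cohort, or experience a DLT during the DLT period".

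**What the SAP declares.** SAP 1.1 lists protocol v3.0 and v4.0 as its basis. SAP 2.1 states one change to the protocol: "Efficacy endpoints will only be listed by subject and timepoint, they will not be summarized in the CSR". SAP 2.2 adds the abbreviated CSR and the removal of the expansion analyses.

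**Where the set is used.** Protocol 11.5.2: "The number treated per FAS, number of DLT evaluable subjects, number of DLTs, and DLT rate on each DL cohort will be tabulated". SAP 6.1: "The number and percentages of subjects in each analysis set as defined in Section 4 will be presented by dose level cohort". SAP 9.1: "DLT will be summarized by PT in order of descending frequency using Dose-Determining Analysis Set". SAP 5.1, as the default for percentages: "the number in the column header (e.g., the number in that cohort, etc.) will be used as the denominator unless otherwise specified".

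**DLT window.** SAP 5.5 fixes the DLT period at Days 1 to 21 and cites protocol 7.1. Protocol 7.1 gives that length for one intermediate dose on schedule, but also allows the period to be adjusted for treatment delay.

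**The concern.** DLTs are a primary endpoint of the Dose Escalation part, and the dose-determining set supplies their denominator. The SAP rule suits prime/full/full dosing, where any two of the three doses include a full dose. Once an intermediate dose is inserted, two doses can be priming plus intermediate, which is the pair a subject has after stopping early. Such a subject, if DLT-free, never received the full dose that defines the cohort, yet can be counted as evidence that it was tolerated.

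The SAP also omits the protocol's timeliness condition, and its fixed 21-day window can close before a delayed full dose has been observed. A reader of the CSR would take the evaluable number to be the protocol's when it follows another rule.

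**Working it through.** The documents give no DLT or evaluable counts by cohort, so there is no planned or observed rate to reproduce. The check is of the definitions, followed by the arithmetic of one added subject.

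**1. Which cohorts can have two doses without a full dose (SAP Table 1).**

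| First full dose is planned | Cohorts | Can 2 of 3 doses omit it? |
|---|---|---|
| second (C1D8) | 0.3/3/3, 1/5/5 | No: all 3 pairs contain a full dose |
| third (C1D15) | 1/3/10, 1/3/30, 1/5/30, 1/10/30, 1/5/45, 1/3/60 | Yes: 1 of 3 pairs, priming plus intermediate |
| fourth (C2D1), as printed | 1/5/30/37.5 | Not counted |

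The rows 1/5/45 and 1/5/30/37.5 carry footnote marks whose text is not available. For 1/5/30/37.5 the last two doses are in parentheses, and SAP 1.2 says at most one intermediate dose was used, so its actual dosing is unclear.

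**2. Timeliness.** This condition can matter in any cohort, including the first two. In 1/5/5 the first full dose is planned for Day 8. Given on Day 17, it is 17 − 8 = 9 days late. It still falls within the SAP's 21 days, so 2 of 3 doses are met. Under protocol 11.1.7 it exceeds the general 7-day limit, and the subject is evaluable only if the DEC accepts the delay.

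**3. Effect on the rate.** Let d be the number of subjects with a DLT, n the protocol-evaluable number, and k the added DLT-free subjects.

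- Protocol rate: d/n. SAP rate: d/(n + k).
- Ratio: n/(n + k), a relative drop of k/(n + k), or 1/(n + 1) for k = 1.

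| Protocol set | SAP set, k = 1 | Relative drop |
|---|---|---|
| 1/3 = 33.3% | 1/4 = 25.0% | 1/4 = 25.0% |
| 2/6 = 33.3% | 2/7 = 28.6% | 1/7 = 14.3% |
| 3/9 = 33.3% | 3/10 = 30.0% | 1/10 = 10.0% |

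If d = 0, the rate stays at 0 and only the evaluable number grows. If k = 0, the exposure rule changes nothing.

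**4. Window.** Under protocol 7.1 a full dose on Day 15 gives a period ending on Day 21, and one on Day 22 gives Day 28 (its own case of two intermediate doses). Now take a one-intermediate cohort with the full dose 7 days late, on Day 15 + 7 = Day 22. The protocol still regards this as timely, and a window tied to the full dose runs to Day 28. The SAP window has closed on Day 21, before the full dose was given. A DLT on, say, Day 25 is outside it, while the subject already has 2 of 3 doses.

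The protocol is itself mixed here. Parts of 4.2, 7.1, 11.1.7 and Table 28 tie the window to 7 days after the first full dose. The end of 4.2, the cohort-size text in 4.2.1.1 and the follow-up test in 11.1.7 use a fixed 21 days (or 28 in 4.2 and 11.1.7 with two intermediate doses).

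**The case against.** **The SAP has other safeguards.** Stopping in Cycle 1 for treatment-related toxicity is itself a DLT under protocol 7.1, so those subjects enter as events. The observation and judgement conditions may exclude some others. Both limit the effect, but neither restores a full-dose requirement. AEs are recorded until 30 days after the last dose (protocol 10.2.1), so a subject last dosed on Day 8 can be followed to Day 38. The judgement asked for is whether a DLT occurred, not whether the full dose was given. The priming-plus-full example does not bind.

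**The text may be a carry-over.** SAP 1.1 lists v3.0, and SAP 3.2 still plans 58 subjects where protocol v4.0 plans about 80. This is plausible, but v3.0 is not available and the SAP assigns no v3.0 rule to any cohort. A carry-over would still need declaring.

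**The protocol is looser than a strict reading.** The 7-day limit applies in general and the DEC may relax it. Protocol 4.2.2 refers to minimum treatment requirements in 7.1 that 7.1 does not state. This stands, but none of it supports a 2-of-3 rule.

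**The data would show it.** SAP 8.2 summarizes the number of full doses and dose delays by cohort, and SAP 5.1 lists subject data by default. Missed full doses would be partly visible, and the protocol set could be rebuilt. That softens the problem without making the labelled number correct.

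**A stronger reading that does not hold.** A reader might infer that the change altered dose recommendations, since adding one subject can cross a boundary in protocol Table 11 (1/4 is remain, 1/5 is escalate). SAP 1.2 records that enrolment has stopped, the SAP plans no escalation decision, and past decisions were taken by the DEC and Safety Committee. Nor do the documents show that any reported rate has in fact been lowered.

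**Conclusion.** The mismatch is real and undeclared, and should be corrected before the CSR tables are final. The missing-full-dose route exists in six cohorts as printed. The missing timeliness condition can change who is evaluable in any cohort, including 0.3/3/3 and 1/5/5.

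The effect on the rate is conditional. It needs at least one DLT and at least one added DLT-free subject in the same cohort; the relative drop is then 1/(n + 1) per added subject, which is 25% at n = 3 and 10% at n = 9. It is nil on the rate where no DLT occurred, and nil altogether if all subjects were dosed as planned. The documents do not show which case applies. They also leave the table layout to the DPS, which is not available, so how prominently a rate appears is unknown.

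The consequence is confined to the reported primary DLT summary. Confidence is high for the difference in definitions, but the size of its effect is unknown.

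**What to change.** 1. In SAP section 4, use the exposure criterion of protocol 11.1.7, including the timeliness condition and the DEC's discretion over longer delays.
2. If the 2-of-3 rule is kept for any cohort, for example those enrolled under v3.0, name those cohorts and declare the rule in SAP 2.1. Footnote the DLT table, and report the protocol-defined evaluable number and DLT rate beside it.
3. In SAP 5.5, state which DLT window applies when the first full dose is delayed. The protocol passages that fix the window from priming must be reconciled with those that tie it to the first full dose.

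The cost is SAP wording, one reprogrammed analysis-set flag and a table footnote. Some cohorts may then show fewer evaluable subjects and higher DLT rates. No new data are needed beyond the dosing dates, DLT records and any DEC decisions on delays.

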5.1 General statistical methods

The statistical analyses will be presented by dose level cohort, for the different analysis sets as defined in Section 4.

In general, continuous variables will be summarised using descriptive statistics, i.e. displaying number of subjects in the respective analysis population, number of subjects with data, number of subjects with missing values, mean, standard deviation, minimum, median, and maximum.

Categorical variables will be summarised by using frequency counts and percentages. In addition, the number of subjects with missing values will be displayed where appropriate. When the number of subjects with non-missing values is displayed by visit (i.e., the number of subjects with a certain assessment completed at a given visit), that number will be used to calculate the percentages for that visit. Otherwise, the number in the column header (e.g., the number in that cohort, etc.) will be used as the denominator unless otherwise specified.

Means, medians, and standard deviations will be presented by 1 additional decimal place more than the standard presentation level of the respective subject data. Minimum and maximum values will be presented using the same number of decimal places as the subject data. Percentages will be presented to 1 decimal place if not otherwise stated.

If the number of subjects in a category is 0, then the percentage will not be displayed, and only a count of 0 will be shown.

Figures will be presented as necessary. Unless otherwise specified, by-visit figures will display information as presented in tables (e.g., based on analysis visit). Time-to-event figures, profile plots, and other figures not based on specific visits will include unscheduled visits.

Unless otherwise specified, all subject data collected as part of this trial (CRF data, laboratory results, etc.) will be presented in data listings. In general, data will be sorted by dose level cohort or tumor type cohort (as appropriate), site, and subject, and when appropriate by visit or other identifiers for sequence or type of observation.

